## 6.5 Participant Withdrawal Criteria

Participants will be advised that they are free to withdraw from the study at any time for any reason or, if necessary, the PI (or delegate) may discontinue a participant from the study to protect the participant's health. A participant may voluntarily withdraw or be withdrawn from the study for reasons including, but not limited to, the following:

- The need to take medication which may interfere with study measurements.
- Intolerable/unacceptable AEs.
- Positive test for Covid-19
- Noncompliance of the participant with the protocol.
- Withdrawal of consent; or
- If, in the PI's (or delegate's) judgement, it is in the participant's best interest.

The Sponsor will be notified as soon as possible of any participant withdrawals. The date and reasons for withdrawal will be recorded in the eCRF and included in the final clinical study report, along with any AEs and necessary medical treatment (up until the point of study withdrawal).

Any participant who prematurely discontinues study drug, should have, if possible, all scheduled safety assessments performed, including all follow-up visit assessments as scheduled. If a participant withdraws from the study, an attempt should be made to collect all remaining safety samples scheduled for that day.

In the event that a participant is discontinued from the study due to an SAE, the PI (or delegate), or medically trained nominee, will evaluate the urgency of the event. If the situation warrants, the PI (or delegate), or medically trained nominee, will take appropriate diagnostic and therapeutic measures and attempt to notify the sponsor's medical expert. If the situation is not an immediate emergency, the PI (or delegate), or medically trained nominee, at the clinical facility will attempt to contact the sponsor's medical expert for consultation. No medical help, diagnosis, or advice will be withheld from the participant due to an inability to contact the sponsor's medical expert. The participant will be encouraged to remain available for follow-up medical monitoring.

Participants who withdraw from the study prior to treatment will be replaced according to recruitment and enrolment processes outlined in [Section 7.3](#).

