2.2 Objectives

2.2.1 Primary Objectives and Endpoints

The primary objective of this study is:

- To determine the safety and tolerability of single and multiple doses of intranasally delivered LMN-301.

The primary endpoints of this study are:

- The occurrence of solicited AEs for 28 days after the first dose of LMN-301.
- The occurrence of unsolicited AE/SAEs for up to 28 days after the first dose of LMN-301.
- Discontinuation.
- Changes from baseline in vital signs, safety laboratory parameters, ECG parameters and nasal symptoms using the Sino-nasal outcome test (SNOT-22).

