4.2 General Considerations

All data collected during the study (data originating from the electronic Case Report Forms (eCRFs) or electronic transfers will be presented in the data listings. Event-based listings will be sorted by treatment group, participant identifier and event start date/time (i.e., AE start date/time). Assessment-based listings will be sorted by treatment group, parameter name (alphabetically unless specifically stated otherwise), participant identifier, visit and time point (if applicable).

Unless otherwise stated, the following methods will be applied:

- Continuous variables: Descriptive statistics will include the number of non-missing values (n), arithmetic mean, standard deviation, median, minimum and maximum values. The minimum and maximum values will be displayed to the same decimal precision as the source data, the arithmetic mean and median values will be displayed to one more decimal than the source data, and the SD values will be displayed to two more decimals than the source data for the specific variable. The appropriate precision for derived variables will be determined based on the precision of the data on which the derivations are based, and statistics will be presented in accordance with the abovementioned rules.
- Categorical variables: Descriptive statistics will include frequencies and percentages per category. The denominator in all percentage calculations will be the number of participants in the relevant analysis population with non-missing data, unless specifically stated otherwise. Percentages will be rounded to one decimal place and will not be displayed for zero frequencies.
- Presentation of p-values and confidence intervals: 95% confidence intervals will be computed, and reported to four significant figures, p-values will be displayed up to three decimal places and as “<0.001” if the value is below 0.001.
- Repeat/unscheduled assessments: Only values collected at scheduled study visits/time points will be presented in summary tables. If a repeat assessment was performed, the result from the original assessment will be presented as the result at the specific visit/time point. All collected data will be included in the data listings. If an unscheduled visit was intended to replace the missing assessment for a scheduled visit this should be documented clearly before values are carried forward as a scheduled visit assessment.

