4.3 Key Definitions

The following definitions will be used:

- Date of the First Study Treatment Administration: The date of the first study treatment administration is defined as the earliest date on which a study treatment was administered.
- Date of the Last Study Treatment Administration: The date of the last study treatment administration is defined as the latest known date on which a study treatment was administered.
- Baseline: The Baseline value is defined as the last available valid, non-missing observation (including repeat and unscheduled assessments) for each Participant prior to first study treatment administration on Day 1.

For ECG triplicates, the baseline is defined as the mean of the last set of triplicates performed prior to first study treatment administration.

For SNOT-22 results, the baseline is defined as the total score (as defined in section XX) of the last SNOT-22 test performed prior to first study treatment administration.

- Change from Baseline: The change from Baseline value is defined as the difference between the result collected/derived at a particular visit and the Baseline value.

The change from Baseline value at each visit will be calculated for all continuous parameters using the following formula:

$$\text{Change from Baseline Value} = \text{Result at specified visit} - \text{Baseline Value}$$

The change from Baseline value will only be calculated if the specific visit result and the Baseline value for the parameter are both available and will be treated as missing otherwise.

- Study Day: The study day of an event is defined as the relative day of the event starting with the date of the first study treatment administration (reference date) as Day 1 (there will be no Day 0).

The study day of events occurring before the first study treatment administration will be calculated as:

Study Day = (Date of Event - Date of First Study Treatment Administration)

For events occurring on or after Day 1, study day will be calculated as:

Study Day = (Date of Event - Date of First Study Treatment Administration) + 1

Study days will only be calculated for events with complete dates and will be undefined for events that are 'Ongoing' at the end of the study.

- Actual Time from First Dose (hours) in PK related outputs is defined as:

$$(\text{Date/Time of PK Sample collection}) - (\text{Date/Start Time of First Dose on Day 1})$$
- Actual Time Deviation (hours) in PK related outputs is defined as:

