4.5 Handling of Missing Data

In general, all data will be analysed as collected and missing values will not be imputed or replaced unless stated otherwise.

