4.6 Treatment Group and Visit Display Conventions

Summary Tables:

In summary tables, the representation as below:

Part A:

- Sentinels (*50mg once only*)

Part B:

- Group 1 (*50mg every 3rd day*)
- Group 2 (*50mg every 2nd day*)
- Group 3 (*50mg daily*)
- Overall (*Part B subjects*)

Data Listings:

In data listings, the following labels will be used:

Part A:

- Sentinels

Part B:

- Group 1
- Group 2
- Group 3

Visit labels:

The following visit labels will be used:

- Screening (Listing only)
- Day 1 (Listing only)
- Baseline (Table only)
- Day 2
- Day 3, Day 4, Day 5, Day 6, Day 7
- Day 8
- Day 9, Day 10, Day 11, Day 12, Day 13
- Day 14
- Day 28
- Early Termination (Listing only)
- Unscheduled (Listing only)

For listings, the visit representing baseline (either screening or unscheduled visit) will be marked as “[1]” with a footnote indicating it is baseline value. These visit displays will be sorted by date of visit within each participant.

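### Post-dose values from unscheduled and early-termination visits reach the listings but not the by-visit change-from-baseline and shift tables

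*SAP*

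**What the plan says.** SAP 4.6 fixes the visit labels for tables and listings. Two of them are "Early Termination (Listing only" and "Unscheduled (Listing only". SAP 4.2 gives the general rule: "Only values collected at scheduled study visits/time points will be presented in summary tables". It allows one exception: "If an unscheduled visit was intended to replace the missing assessment for a scheduled visit this should be documented clearly", after which the value may stand as that scheduled visit's result. SAP 4.5 adds that "missing values will not be imputed or replaced unless stated otherwise".

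These rules govern the tables for part of the primary endpoint. SAP 2.2.1 lists change from baseline in vital signs, safety laboratory tests, ECG and SNOT-22. SAP 13.2, 13.3 and 13.4 tabulate their parameters at baseline and at each scheduled post-baseline visit, and SAP 13.7 summarises the SNOT-22 total under the SAP 4.2 rules. Shift tables, also by visit, are planned for haematology, chemistry, coagulation and vital signs, but not for ECG. Normal/NCS/CS counts are planned for vital signs, ECG and urinalysis. No table has a row that combines all post-baseline values.

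Protocol 6.5 names "Intolerable/unacceptable AEs" among the reasons for leaving the study.

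**The concern.** Safety and tolerability are the primary objective, and SAP 13 analyses everyone dosed. An unscheduled visit may be prompted by a symptom or a laboratory worry, and an exit visit may follow an intolerable event. Values from such visits are more likely than routine ones to be abnormal, yet the display rule keeps them out of the tables a reader looks at first. After a participant leaves, each later row describes those who remained. Where leaving is linked to tolerability, the row tends to look better than the experience of the whole group. In groups of 10, one omitted abnormal value can decide whether a shift cell is empty.

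The issue is how collected values are tabulated, not whether they are collected. The SAP's own early-termination label shows that such records are expected.

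**Working it through.** **1. The plan's own figure.** SAP 3 uses an SAE probability of 10%. The chance of at least one event in n participants is 1 − (1 − 0.10)^n.
- n = 35: 1 − 0.9^35 = 97.50% (stated: over 97%).
- n = 30: 1 − 0.9^30 = 95.76% (stated: over 95%).

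Both reproduce. They concern SAEs and say nothing about how many participants leave.

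**2. Where each value goes under SAP 4.2, 4.3 and 4.6.**
- Scheduled visit attended before exit: table and listing.
- Unscheduled or repeat value before the first dose: can be the tabulated baseline.
- Unscheduled value after dosing, documented as replacing a missed scheduled assessment: table and listing.
- Any other unscheduled value after dosing: listing only.
- Value filed under early termination: listing only.

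**3. Where the gap is widest.** Protocol Tables 21-A and 21-B schedule ECG and urinalysis at Screening and End of Study only (Day 14 in Part A, Day 28 in Part B). A participant who leaves before then has no tabulated post-baseline result for either, even if one was obtained at exit. Vital signs and laboratory tests have several scheduled post-baseline visits, so an early leaver usually keeps some rows.

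**4. Shift-table illustration.** Assume a group of 10, no replacement, and no High values except at exit. SAP 4.2 uses participants with non-missing data as the denominator.
- One leaver, High at exit: later visit rows show 0/9 = 0.0%. Counting the exit value gives 1/10 = 10.0%. In the Part B overall column this is 0/29 against 1/30 = 3.3%.
- Two leavers, both High at exit: 0/8 against 2/10 = 20.0%. Overall, 0/28 against 2/30 = 6.7%.

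Protocol 7.3 allows participants who leave after dosing, other than for an SAE, to be replaced in the same group. With one leaver replaced, the row could read 0/10 against 1/11 = 9.1%, and the row count would not show that anyone had left.

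**5. How often a group would have a leaver.** The leaving rate r is assumed, because the documents give none. The chance is 1 − (1 − r)^n.

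| r | n = 10 | n = 30 |
|---|---|---|
| 3% | 26.3% | 59.9% |
| 5% | 40.1% | 78.5% |
| 10% | 65.1% | 95.8% |
| 20% | 89.3% | 99.9% |

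These are chances that someone leaves for any reason. The chance that an abnormal exit value exists and goes untabulated is lower by an unknown amount.

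**6. SNOT-22 illustration.** Assume that nine participants average +2, that one leaves at +15, and that an exit score was taken. The visit row shows +2.0. Counting the exit score gives (9 × 2 + 15)/10 = 3.3, a difference of 1.3 points. The total runs from 0 to 22 × 5 = 110, so this is 1.3/110 = 1.2% of the range.

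**The case against.** The strongest reply is that the SAP follows the protocol and that leavers are visible elsewhere. Protocol 13.7.2, 13.7.5, 13.7.6 and 13.7.7 call for summaries at scheduled timepoints. Disposition tables and the treatment-emergent AE tables, including events leading to study withdrawal, are not by visit and count every leaver. Clinically significant laboratory, vital-sign and ECG findings become AEs. Nasal symptoms are asked about directly and tabulated as solicited AEs. The listings show change from baseline at unscheduled visits and can be read in full at 5 or 10 per group. All of this stands and limits the harm. It does not put an exit value into a shift table, and the SNOT-22 total score has no AE route of its own.

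Second, few exit values may exist. Neither schedule contains an early-termination visit. At withdrawal, Protocol 6.5 asks only for an attempt at that day's remaining safety samples, and nothing requires an exit SNOT-22 or ECG. Those who stop study drug but stay in the study should, if possible, complete all scheduled assessments, and these are tabulated normally. This also stands, and it is why no size can be fixed.

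Third, a reader might infer that the rule always flatters the drug. The documents do not support that. Participants may also leave after a positive COVID-19 test, for noncompliance, by withdrawing consent or because they need other medication. SAP 4.2 also keeps the first reading over a repeat, which can leave an abnormal result in the table.

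**Conclusion.** The point holds for the by-visit change-from-baseline tables, the laboratory and vital-sign shift tables, and the by-visit Normal/NCS/CS counts. A stated rule, not a missing detail, leaves post-dose unscheduled and exit values untabulated unless they are documented replacements. It affects each leaver from exit onward, and it affects any participant whose abnormal value was seen only at an unscheduled visit.

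Its size is unknown. The 0/9 against 1/10 contrast follows from the rule once one such value is assumed. The leaving rates and SNOT-22 scores are assumptions.

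Two stronger readings are tempting. One is that leavers vanish from every safety table. They do not: AE and disposition tables and earlier visit rows keep them. The other is that the plan expects 10% to leave, or that SNOT-22 means would be badly understated. The 10% is a hypothetical SAE rate, and a large percentage error in the SNOT-22 example would only reflect an assumed mean close to zero.

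No sample-size or error-rate figure changes. This is an inexpensive improvement to the reporting of a primary safety endpoint.

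**What to change.** Keep all by-visit rows. In SAP 4.2 and 4.6, define one added row, *Worst post-baseline (scheduled, unscheduled and early-termination)*, and include it in:
- the laboratory and vital-sign shift tables;
- the Normal/NCS/CS counts for vital signs, ECG and urinalysis;
- the SNOT-22 total-score table.

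The denominator is every Safety Analysis Set participant with any post-dose value for that assessment. State that Day 1 post-dose readings count, because SAP 4.6 also labels Day 1 as listing only. Amend the early-termination and unscheduled labels to match, and record the addition in SAP 16. If the database is already locked, SAP 1 allows the row to be reported as an additional analysis described in the CSR.

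A last on-study value row is optional. It would mix early exits with Day 28 completers, and SNOT-22 asks about the preceding two weeks.

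The cost is SAP wording and one row per table, with no new data. The downside is that a worst-value row rises with the number of readings. That number differs between Parts A and B and, through unscheduled visits and early exits, can differ among the Part B groups. The row should be read beside the by-visit rows, with the number of readings noted.

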5 ANALYSIS POPULATIONS

5.1 Full Analysis Set (FAS)

The Full Analysis Set will include all enrolled participants.

5.2 Safety Analysis Set (SS)

The Safety Analysis Set will include all participants who receive study drug and will be analyzed as per the treatment group they were assigned to.

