## 6.7 Treatment Allocation

All study participants who sign an informed consent form at screening will receive a unique sequential number (i.e., a screening number). Participants will be allocated to the next available treatment group in the order they are screened. As this is an open-label study, no randomisation or blinding will occur.

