**Figure 8-A Unidose Nasal Device**

Each Unidose nasal device delivers a dose of 25 mg. Detailed instructions are provided in the study Pharmacy Manual.

The total dose to be delivered will be divided equally across both nostrils, with a total of 1 actuation per nostril required for each dose, i.e., a total dose of 50 mg (See [Table 8-A](#)).

All dosing will take place in the clinical facility under the supervision of site staff.

Participants in study Part A (sentinel cohort) will be observed as in-patients for 24 hours after administration of study drug.

Participants in study Part B (multiple dose cohort) will be observed on site for 4 hours after administration of the first dose.

- Participants in Group 1 will return to the site every 3rd day (Days 4, 7 and 10) for dosing and safety monitoring
- Participants in Group 2 will return to the site every 2nd day (Days 3, 5, 7, 9 and 11) for dosing and safety monitoring
- Participants in Group 3 will return to the site daily (Days 2 to 12) for dosing and safety monitoring

Details of dose administration will be recorded in the eCRF.

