#### Safety Analysis Set

All participants who receive any study drug will be included in the Safety Analysis Set and will be analysed as per the actual treatment received, if this differs from that to which the participant was randomised.

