### *13.7.6 Electrocardiogram*

For ECG data, replicate values will be averaged to determine the value of the ECG parameter at each timepoint.

The following ECG parameters will be analysed: PR interval, QRS duration, QTcB, QTcF and ventricular heart rate. Observed values and changes from baseline for ECG parameters will be summarised at each scheduled timepoint using descriptive statistics.

For QTcF, the number of participants with values greater than 450 (and 480, 500) msec or an increase from baseline of at least 30 (and 60) msec will also be tabulated, in accordance with ICH E14 (Note for guidance on the clinical evaluation of QT/QTc interval prolongation and proarrhythmic potential for non-antiarrhythmic drugs, CHMP/ICH/2/04).

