12 TREATMENT COMPLIANCE AND EXPOSURE

All study drug administration information (study drug administered [Yes/No], study day, reason not administered, fasting status, reason for not fasting, date and time of administration, dose [mg]) will be listed by treatment groups defined in section 4.6, sorted by participant ID and study day for the SS population.

Treatment Compliance during the treatment period is defined as:

$$\frac{\text{Total number of doses administered}}{\text{Expected number of doses based on the treatment regimen received}} * 100\%$$

The total number of tablets administered for each treatment is defined as:

- Part A:
 - Sentinels: 1 dose
- Part B:
 - Group 1: 4 doses
 - Group 2: 6 doses
 - Group 3: 12 doses

Treatment Exposure during the treatment period is defined as:

$$\text{Date of last dose of study drug} - \text{Date of first dose of study drug} + 1$$

Treatment compliance and exposure rates will be summarised using descriptive statistics by treatment groups defined in section 4.6 for the SS population. Treatment compliance and exposure rates will also be listed by treatment groups defined in section 4.6, sorted by participant ID for the SS population.

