13.4 Electrocardiogram (ECG)

The following ECG measurements will be taken at the time points specified in the study procedure schedule (section 20):

- Heart Rate (bpm) [Reference range: 45-100 bpm]
- PR interval (msec) [Reference range: 120-220 msec]
- QRS duration (msec) [Reference range: <120 msec]
- QTcB & QTcF internal (msec) [Reference range: ≤470 msec (females), ≤450 msec (males)]
- Overall Investigator Finding
 - Normal
 - Abnormal NCS
 - Abnormal CS

The mean/average of ECG triplicates at applicable visit/timepoints for each participant will be derived and displayed in the data listing along with the original triplicates. For ECG interpretation, the worst ECG triplicate will be used and displayed in the mean of ECG triplicate.

In summary tables, the mean of ECG triplicates will be used, and the baseline of ECG triplicates will be as defined in section 4.3.

Summary statistics for ECG parameters in accordance with section 4.2 will be presented for baseline and for each scheduled post baseline visit (which also includes the change from baseline). In addition, clinical result of ECG interpretation (Normal, Abnormal NCS, and Abnormal CS) will be summarized by counts and percentages for baseline and for each scheduled at post baseline visit. These summary tables will be generated using the SS population for treatment groups defined in section 4.6.

The listing of ECG parameters will include all the information collected. In addition, the observations that are used as the baseline record (value) for each parameter will be flagged, and the change from baseline values at each post baseline (scheduled and unscheduled) visit will be presented. This listing will be presented by treatment groups defined in section 4.6, sorted by participant ID and visit for the SS population, along with the age, sex, race and baseline weight of the participant.

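### The SAP groups the safety set by assignment rather than treatment received and omits the protocol's QTcF threshold counts, and declares neither change

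*SAP*

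**What the plan says.** **Grouping.** Under Protocol 13.2, participants in the Safety Analysis Set "will be analysed as per the actual treatment received, if this differs from that to which the participant was randomised". Under SAP 5.2 they "will be analyzed as per the treatment group they were assigned to". SAP 13 uses this set for every safety endpoint. Protocol 6.7 adds that "As this is an open-label study, no randomisation or blinding will occur", so the protocol's reference to randomisation does not fit its own design. SAP 12 takes yet another basis for compliance, with the denominator given as "Expected number of doses based on the treatment regimen received".

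**QTcF.** Protocol 13.7.6 says the number of participants with QTcF "greater than 450 (and 480, 500) msec or an increase from baseline of at least 30 (and 60) msec" will be tabulated. SAP 13.4 plans descriptive statistics for values and changes from baseline, a listing with triplicates and their means, and one categorical output: "clinical result of ECG interpretation (Normal, Abnormal NCS, and Abnormal CS) will be summarized by counts and percentages". Neither SAP 13.4 nor any other SAP section plans the threshold counts.

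**Declared changes.** SAP 16 has a single entry, for Protocol 13.6 (compliance and exposure shown on the safety set only).

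**The concern.** The two grouping rules are opposites, and they govern the tables that answer the primary objective. The three Part B groups receive the same product at the same dose and differ only in how often it is given, so the group columns are the comparison of dosing frequencies. If a participant followed another group's schedule, the SAP rule would report that participant's events under a frequency they did not have.

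For QTcF, the planned outputs do not stand in for the missing table. The upper reference limit in SAP 13.4 is 470 msec for women and 450 msec for men. A woman at 451 to 470 msec, or anyone whose QTcF rises by 30 to 59 msec and stays in range, need not be classed as abnormal. The maximum shows one extreme per group, and no planned table says how many participants crossed each threshold. ECG change is part of the primary endpoint. By way of context, SAP 13.2 and 13.3 give laboratory values and vital signs low/normal/high shift tables, while ECG gets no table that categorises its measured values.

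A SAP may depart from a protocol. The difficulty is that the section set aside for recording departures is silent on both, so a reader of the SAP would not know that they exist.

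**Working it through.** The plan states no figure on this point that could be reproduced. The check compares the texts and works out what each difference could do to a table.

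**1. Text comparison**

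| Item | Protocol | SAP | In SAP 16? |
|---|---|---|---|
| Safety set grouping | Treatment received (13.2) | Assigned group (5.2) | No |
| QTcF >450, >480, >500 msec; rise ≥30, ≥60 msec | Counts tabulated (13.7.6) | No counts (13.4) | No |
| Compliance and exposure set | Safety and full sets (13.6) | Safety set only (12) | Yes |

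**2. Effect of one crossover**

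Inputs: 10 participants per Part B group and 30 in Part B (Protocol 6.3). Suppose one participant assigned to one group is dosed on another group's schedule and has an event, and nobody else in those two groups has it.

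- By assignment: assigned group 1/10 = 10.0%, receiving group 0/10 = 0%. Difference +10.0 points.
- By treatment received: assigned group 0/9 = 0%, receiving group 1/11 = 9.1%. Difference -9.1 points.
- Part B overall, with no event in the third group either: 1/30 = 3.3% under both rules.

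If k others in the assigned group have the event, that group's figure differs between the rules by

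(k+1)/10 - k/9 = (9 - k)/90.

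This is 10.0 points at k = 0, 6.7 points at k = 3 (40.0% against 33.3%) and 0 at k = 9. With no crossover the two rules give identical tables.

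**3. Compliance under crossover**

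SAP 12 expects 4 doses in Group 1 and 6 in Group 2. A Group 1 participant given all 6 doses of the Group 2 schedule would score 6/6 = 100% for the regimen received, yet SAP 5.2 would place that result in the Group 1 column. The two SAP sections conflict only in this situation.

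**4. What the QTcF table would rest on**

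Protocol 11.14 schedules ECGs at Screening and End of Study, so each participant has one scheduled post-dose ECG. End of Study is Day 14 in Part A and Day 28 in Part B. Nominal time from the last scheduled dose:

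- Part A: 14 - 1 = 13 days
- Group 1: 28 - 10 = 18 days
- Group 2: 28 - 11 = 17 days
- Group 3: 28 - 12 = 16 days

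**5. What the planned ECG table can hide**

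As an illustration with assumed values, take two women in one group at 455 and 460 msec, everyone else being at or below 450. The protocol's table would show 2/10 (20%) above 450 msec. In the SAP's table the maximum of 460 would reveal that 450 had been passed, but not by how many participants. Both women are within the female reference range.

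**The case against.** The strongest reply is that little is lost in practice. On grouping, all groups get the same 50 mg dose from the same device, groups are filled in sequence, and "All dosing will take place in the clinical facility under the supervision of site staff". Crossover is unlikely, nothing in the documents suggests it happened, and the 19.1-point swing (+10.0 to -9.1) needs the crossover participant also to have the only event. Assigned group is a clear rule, whereas regimen received needs defining when groups differ only in frequency. On QTcF, with 35 planned participants and one scheduled post-dose ECG well after dosing, every threshold can be counted by hand from the listing. Inclusion criterion 5 excludes QTcF prolongation at entry, and the protocol expects low systemic exposure. The protocol synopsis mentions only descriptive statistics for ECG, and Protocol 13 describes itself as a general framework open to revision.

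Most of this stands as a limit on size, and it shows why the point is not a serious threat to the trial. It does not remove the defect. The intent of Protocol 13.2 is plain despite the misplaced word. Protocol 13.7.6 is specific and says the counts will be tabulated; a listing that can be counted by hand is not that table. Protocol 13.7.6 asks for no ECG shift table, so the absence of one is context and not a departure. As for declaration, SAP 16 already lists a change that it says makes no difference between the two sets, so by the sponsor's own practice a departure is recorded even when it has no numerical effect.

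One doubt remains. The SAP cites protocol Version 1.0 of 25 May 2023, and the protocol text available here does not confirm its version. SAP 16's account of Protocol 13.6 does match that text, which makes a version mismatch an unlikely explanation.

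**Conclusion.** The concern holds in all three parts: the SAP's grouping rule contradicts the protocol's, a table promised by the protocol is missing, and neither departure is declared. Both should be corrected, though no effect on the trial's overall safety conclusion has been shown.

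For grouping, the effect is zero without crossover. At most, for one crossover participant with the only event, the assigned group's rate changes by 10.0 points and the sign of the difference between the two groups reverses. This assumes full groups of 10. The QTcF omission applies whatever the data show, but the information lost is modest: threshold counts at one late visit, with individual values still listed.

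**What to change.** - **SAP 5.2:** analyse the safety set according to the regimen actually received. State that a missed dose does not by itself change the regimen, so that only a participant dosed on another group's schedule is regrouped. Say also how a participant who switches part-way is classified.
- **Protocol 13.2:** replace *randomised* with *assigned*.
- **SAP 13.4:** add the QTcF table (>450, >480, >500 msec; increase ≥30, ≥60 msec) from triplicate means, for Part A, each Part B group and Part B overall. Footnote that it rests on one scheduled post-dose ECG per participant.
- **Alternative:** if the sponsor prefers the SAP as it stands, list both departures in SAP 16 with reasons.

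The cost is a few sentences and one table in the SAP and one word in the protocol. No new data are needed.
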